3.3.2 Retention

Retention will be maximized by reimbursing participants for their time spent on the 4-week and 1-week reassessments (\$30, \$30, respectively) and by providing an additional \$20 for completion of dietary recall measures. Study staff will ask permission to collect multiple phone numbers, email addresses, and family or close friend contact information, and assess preferences for contact methods. Reminder text messages/emails will be sent prior to the remote evaluation visits and follow up with participants via various channels (text, phone, email) if they have yet to complete assessments.

3.3.3 Participant Eligibility Criteria

| | |
|--------------------|--|
| Inclusion Criteria | 
• adults (ages 18+ years)• body mass index (BMI) 25.0 to 45.0 kg/m²• smartphone ownership• willingness to install the Fitbit mobile app on their phone• access to a personal email account• English language proficiency• interest in losing weight through behavioral strategies• Living in the United States |
|--------------------|--|

| | |
|--------------------|--|
| Exclusion Criteria | 
 • concurrent enrollment in another weight management intervention • loss of ≥ 10 lbs. in the past 6 months • current use of a weight loss medication • prior or planned bariatric surgery • current or planned pregnancy in the trial period • currently breastfeeding • lives with someone else participating in the study • hospitalization for a mental health condition in the past 12 months • inability to engage in moderate forms of physical activity akin to brisk walking • if weight loss is contraindicated or might be impacted by a condition or medication (e.g., end stage renal disease, cancer, schizophrenia, dementia, steroids, anti-psychotics) • if an individual would be better suited for a more intensive or different type of intervention based on a health condition (e.g., individuals with history of an eating disorder or cardiovascular event, uncontrolled hypertension, or uncontrolled diabetes mellitus) • investigator discretion for safety reasons |
|--------------------|--|

3.3.4 Screening and randomization

Recruitment materials will direct interested individuals to an online screening questionnaire (REDCap) that describes the study and assesses initial eligibility. Eligible candidates will then receive an email invitation to sign up for an initial remote visit and

complete an interactive orientation video. At this visit, trained study staff will confirm eligibility and describe study procedures. If individuals are interested in participating, study staff will obtain informed consent to assure that they fully understand the demands and nature of the study before enrolling. Next, study staff will help participants create a Fitbit account, and administer online baseline measures. Once completed, participants will be randomized to 1 of 16 experimental conditions via an algorithm on REDCap. Study staff will mail all participants an e-scale to obtain weight measurement along with a Fitbit activity monitor. Staff will email instructions for setting up the Fitbit app and syncing the e-scale and activity monitor devices, and provide the assigned intervention and corresponding program materials. Staff will troubleshoot, as needed.

3.3.5 Screen Failures

Participants who consent but then become ineligible prior to randomization will be asked to withdraw from the study and will not be randomized. Examples would include if a participant's baseline weight collected via the study-issued scale (after consenting) puts them out of range on the BMI criterion (i.e., no longer being in the 25.0-45.0 kg/m² range), or if a participant reports a pregnancy or exclusionary medical condition in the period between consent and randomization. All other reports of changes to eligibility criteria will be decided upon by study investigators prior to randomization.

3.3.6 Withdrawal/Termination Criteria

If after randomization and during the study period the participant no longer meets certain eligibility criteria, they will be asked to withdraw from the study. This includes

the following: if a participant becomes pregnant during the study; finding out that certain criteria were falsified or not reported (e.g., initial age, initial BMI, concurrent enrollment in another weight management intervention, a health condition that contraindicates weight loss or requires more intensive treatment), or investigator discretion for safety reasons.

Participants who become pregnant during the study period will be asked to leave the study. Changes in health behaviors and weight may not be healthy for a baby during pregnancy. Note that if a participant begins use of an antiobesity medication during the study, they will *not* be asked to withdraw from the study.

3.4 Core Intervention

All participants will receive a core intervention consisting of the following empirically- and theoretically- supported components shown to promote self-monitoring engagement:

Fitbit mobile app:

We will leverage an existing state-of-the-art app from Fitbit that is freely available on iPhone and Android platforms. At baseline, participants will install the mobile app.

Weight loss goal:

All participants will receive a goal to achieve 5% weight loss by 10 weeks, which is consistent with obesity treatment guidelines and equates to 0.5-2 lbs weight loss/week.

Self-monitoring diet:

Participants will be instructed to self-monitor their dietary intake daily via the Fitbit mobile app. This app allows users to track all foods and beverages consumed using a

built-in nutritional database, barcode scanner, or manual entry of individual recipes, and to view graphically their change in caloric intake.

Self-monitoring steps:

Participants will be instructed to self-monitor their step count daily via a wrist-worn Fitbit activity monitor (Fitbit Inspire 3). The Fitbit activity monitor will be synced with the Fitbit app to allow participants to view their progress towards the step goal.

Self-monitoring weight:

Participants will be instructed to self-monitor their body weight daily via a wireless e-scale (the Fitbit Aria Scale). The e-scale will be synced with the Fitbit mobile app, providing real-time graphical feedback.

Self-monitoring eating window:

Participants will be instructed to self-monitor their prior day's eating window (start and stop times) every morning via a brief web-based survey (REDCap). They will receive immediate feedback as to whether they met their goal.

Self-monitoring Red Zone Foods:

Participants will be instructed to self-monitor their Red Zone Foods (highly caloric foods of limited nutritional value, such as ice cream and soda) via a brief web-based e-checklist (REDCap). They will receive this e-checklist daily in weeks 1 and 10 and weekly in weeks 2-9. They will receive immediate feedback as to whether they met their goal.

Tailored feedback:

Each week, participants will receive an email with tailored feedback pertaining to their progress on their assigned self-monitoring goals (described below) and other

intervention components. Feedback will be automatically generated using Microsoft Office's Mail Merge feature.

Behavioral skills training:

Each week, participants will receive an email with theory-informed skills training materials that include structured behavioral lessons on nutrition and physical activity as well as corresponding action plans. These materials will be adapted from our recent trials as well as from gold standard weight loss curricula. Lessons include topics such as reading nutrition labels and promoting physical activity. Embedded in this email will be a link to a brief action plan survey (Qualtrics) that incorporates motivational interviewing and problem-solving strategies. Specifically, participants will be prompted each week to reflect on their current behaviors and areas for change, generate actionable steps to change, identify confidence in doing so, and brainstorm potential barriers and support people

3.5 Experimental Intervention Components

Participants will be randomized to 1 of 16 conditions (**Table above**) that vary in their receipt of harder vs. easier goals across 4 goal domains. A 2^4 full factorial design will allow for all combinations to be tested.

Calorie goal (easier vs. harder). It is common in behavioral obesity treatment to assign a tailored calorie goal based on an individual's baseline height, weight, sex, age, and normal activity level, with a minimum of 1200 Calories (kcal)/day for women and 1500 kcal/day for men, based on national guidelines. In this pilot study, participants will be randomized to receive either an *easier* calorie goal (i.e., the tailored calorie goal plus

250 extra calories in daily budget) or a *harder* calorie goal (i.e., the standard calorie goal as is).

Step goal (easier vs. harder). In the baseline survey, participants will complete the Godin Leisure-Time Exercise Questionnaire that will provide a leisure score index to be used determine their baseline activity level. Scores of 0-13 (interpreted as “Insufficiently Active”) will be assigned a baseline goal of 5,000 steps per day, scores of 14-23 (“Moderately Active”) will be assigned a baseline goal of 7,000 steps per day, and scores ≥ 24 (“Active”) will be assigned a baseline goal of 10,000 steps per day. Participants will be randomized to receive either an *easier* step goal (i.e., this baseline step goal as is) or a harder step goal (i.e., this baseline step goal plus 1,500 steps). Beginning in week 2, this step goal will adapt each week based on the prior week’s progress. Participants will receive a daily step goal of either the 40th (if easier) or 60th (if harder) percentile of the prior week’s daily step count, rounded up to the nearest 500 steps.

Eating window goal (easier vs. harder). Limiting eating windows is the crux of time restricted eating. Participants who receive the easier version of this goal will be instructed to eat within a 12-hour window every day, while those receiving the harder version will be instructed to eat within a 9-hour window every day. Participants will be able to self-select at baseline their preferred eating window (e.g., 9 AM to 9 PM for someone in the easier version, or noon to 9 PM for someone in the harder version).

Red Zone Food goal (easier vs. harder). Limiting Red Zone Foods is intended to help lower caloric consumption, aiding in weight loss. Participants who receive the easier version of this goal will be instructed to eat no more than 5 Red Zone Foods every day,

while those receiving the harder version will be instructed to eat no more than 1 Red Zone Food every day.

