3.6 Outcomes

3.6.1 Overview of Measures

The primary outcomes of this pilot study relate to the feasibility and acceptability of the various goals and their intensity levels. We will compare these outcomes to our a priori benchmarks listed in the **Table** below. Additional exploratory outcomes are also included in this table, and marked with an asterisk. The planned primary outcome for the subsequent fully-powered optimization trial is weight change. We will collect data on weight change in our pilot study. Based on prior research of digital weight loss interventions, we have set benchmarks for the 3% and 5% thresholds, which have been associated with improved cardiometabolic health. We will measure body weight using smart scales (Fitbit Aria Air) that automatically transmit data to the research team. The smart scales will be mailed to participants. Participants will be provided with best practices prior to each weight assessment: calibrate upon arrival; weigh in the AM without clothing, before eating/drinking, and after voiding. We will also administer behavior change measures that will be used in the subsequent optimization trial. In particular, dietary recalls will be measured using the Automated 24-Hour (ASA-24) Dietary Assessment Tool and physical activity will be measured using the GLTEQ self-report measure as well as objectively via the Fitbit Inspire 3 activity tracker to evaluate step count. We will also assess perceived ease of the goals.

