3.6.2 Table of Benchmarks

| Feasibility and Acceptability Metric | Benchmark to meet |
|---|-------------------|
| Intervention engagement over 10 weeks | |
| % days of self-monitoring body weight, steps, dietary intake (assessed separately) | 75% |
| % days of self-monitoring eating window* | 75% |
| % days of self-monitoring Red Zone Foods (when instructed to do so)* | 75% |
| % action plans completed; feedback emails read; lessons reviewed (assessed separately)* | 80% |
| Goal attainment over 10-week intervention | |
| % of days meeting the daily calorie goal | 75% |
| % of days meeting the daily step goal | 75% |
| % of days meeting the daily eating window goal | 75% |
| % of days meeting the daily Red Zone Food goal (when instructed to track them) | 75% |
| % of days meeting the daily protein goal* | 75% |
| Recruitment, retention, and survey completion | |
| % enrolled among those eligible from the online screen* | 50% |
| % retention at 4 weeks*, 10 weeks | 80% |
| % survey completion at baseline, 4 weeks*, 10 weeks | 80% |
| Acceptability | |
| % of participants who would recommend the weight loss program to a friend who is trying to lose weight | 80% |
| % of participants who indicated the [] goal was moderately , very , or extremely helpful (separately for all goals: calorie, steps, eating window, Red Zone Foods, protein, 10-week weight loss, weekly weight loss)* | 80% |

| | |
|---|------------------------------|
| % of participants who indicated that tracking [] was moderately, very, or extremely helpful (assessed separately for all self-monitoring domains: weight, food, steps, weight)* | 80% |
| % of participants who indicated that receiving a personalized progress report, lesson, action plan (assessed separately) was moderately, very, or extremely helpful * | 80% |
| Clinically significant weight loss | |
| ≥ 3% weight loss at 10 weeks* | At least 50% of participants |
| ≥ 5% weight loss at 10 weeks* | At least 33% of participants |

* indicates exploratory outcome (not reported on clinicaltrials.gov)

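### The 75% step-goal attainment row cannot show feasibility by itself: from week 2 the goal follows the participant's own prior week, and the handling of untracked days is not stated

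*Combined protocol and SAP*

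**What the plan says.** **The goal.** In section 3.5 the week-1 step goal is 5,000, 7,000 or 10,000 by activity score, plus 1,500 at the harder level. From week 2 the rule is relative to the participant: "Participants will receive a daily step goal of either the 40th (if easier) or 60th (if harder) percentile of the prior" week's daily step counts, "rounded up to the nearest 500 steps". It governs 9 of 10 weeks, or 63 of 70 days.

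**The benchmark.** The row in section 3.6.2 reads "of days meeting the daily step goal | 75" (per cent). It makes no distinction between levels, and the figure is the same as for the calorie, eating window and Red Zone goals, which have no weekly reset. The row carries no asterisk; an asterisk "indicates exploratory outcome (not reported on clinicaltrials.gov". Section 3.6.1 says: "The primary outcomes of this pilot study relate to the feasibility and acceptability of the various goals and their intensity levels".

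**Day counting.** The Red Zone row defines its days: "of days meeting the daily Red Zone Food goal (when instructed to track them". The step row does not. Neither 3.5 nor 3.9 says whether untracked days enter the percentile or the denominator. The tracking row, "days of self-monitoring body weight, steps, dietary intake (assessed separately", has a benchmark of 75%, so it accepts 25% untracked days.

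**Use.** Section 3.9 compares the metrics descriptively with the benchmarks. Section 2.1 makes a later efficacy trial conditional on feasibility and acceptability being established.

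**The concern.** A fixed goal can be met more often as behaviour improves. A goal that moves with the participant's own recent walking keeps returning the score towards a level set by the percentile. Attainment in weeks 2-10 is then mostly a measure of this week against last week, and two levels with different percentiles have different expected scores before anyone responds. Set beside a single 75%, a shortfall could be taken as evidence that a step goal is not feasible when much of it comes from the rule.

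Two further effects follow. The easier-harder difference in attainment, which section 3 lists among the things to be examined, contains a part that exists without any response. And because untracked days have no stated treatment, the same recorded data could give quite different values of a row that is not exploratory.

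**Working it through.** **Inputs from the documents.** 40th and 60th percentiles, 7 prior days, rounding up to 500, week-1 goals as above, 75% attainment benchmark, 75% tracking benchmark, 16 participants per level (32/2). The 75% has no stated derivation, so there is no plan figure to reproduce.

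**Assumptions.** The documents give neither mean daily steps nor day-to-day variation, nor a percentile formula. Unless stated: independent log-normal days, means 5,000-10,000, CV 25-50%, linear interpolation. Results are given as easier / harder.

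**1. Without rounding.** For 7 past days and one new exchangeable day, the chance that the new day reaches the k-th smallest past value is 1 - k/8. The interpolated percentile sits at rank 1 + 6p: 3.4 for p = 0.40 and 4.6 for p = 0.60.
- Easier: 1 - 3.4/8 = 57.5%
- Harder: 1 - 4.6/8 = 42.5%

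Interpolation makes this approximate; simulation gave 57.3% / 42.0%. The built-in gap is about 15 points.

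**2. With rounding up, full wear, unchanged walking, weeks 2-10 (simulated).**
- Main assumptions: 50-55% / 35-40%.
- CV 15%: 45-51% / 31-37%.
- Two other percentile formulas: 52-60% / 31-38%.
- Overall: about 45-60% / 30-40%. Week-level correlation of 0.2-0.4 moves the full-wear rates by about 1-3 points.

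**3. A steady rise.** Mean 7,000, CV 35%, plus 500 steps/day each week: 9 x 500 = 4,500, and 4,500/7,000 = 64% by week 10. Over 10 weeks attainment is 58.2% / 42.7%, against 52.1% / 36.8% with no change, a gain of about 6 points at each level. The fixed week-1 goal is met on 74% / 55% of days in weeks 2-10. With unchanged walking it would be met on 43% / 23%: with log-SD s = sqrt(ln(1 + 0.35^2)) = 0.34, these are 1 - Phi(s/2) for 7,000 and 1 - Phi(ln(8,500/7,000)/s + s/2) for 8,500.

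**4. A goal-directed response.** Some short days are topped up exactly to the goal (mean 7,000, CV 35%, full wear).
- Half topped up: attainment 70% / 61%, while week-10 steps are +8% / +16%. The level that walks more scores lower.
- 60% topped up at the easier level: about 75%.
- 70% topped up at the harder level: about 76%.

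**5. Untracked days.** 25% untracked at random, unchanged walking, mean 7,000, CV 25-50%, weeks 2-10:

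| Untracked days in the percentile | Days scored | Easier | Harder |
|---|---|---|---|
| Left out | Worn days | 51-53% | 38-40% |
| Left out | All days (untracked = not met) | 38-40% | 28-30% |
| Zeros | All days | 55% | 39-40% |
| Zeros | Worn days | 73-74% | 52-54% |

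Under the last rule the easier level scores about 70-71% over all 10 weeks. If untracked days count as not met, a participant tracking exactly 75% of days reaches 75% attainment only by meeting the goal on every tracked day (0.75 x 1 = 0.75).

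**The case against.** The strongest reply is that unchanged walking is not what the intervention expects. Participants see their progress towards the goal and receive weekly tailored feedback; the row measures adherence to an assigned goal, and a goal met on 75% of days with no response would be a weak one. This stands. Step 4 shows that 75% corresponds to topping up roughly 60-70% of short days, so a reader who infers that the benchmark is unattainable by construction goes too far. A demanding benchmark is a legitimate choice.

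It is also fair that an easier goal should be met more often; that is the manipulation. The documents never say that the two levels will be pooled, and section 3 lists perceived ease and physical activity with goal attainment among the effects to be examined. Section 3.6.1 plans to measure steps "objectively via the Fitbit Inspire 3 activity tracker to evaluate step count". But 3.9 does not set these beside attainment and gives no reference against which to read 75%.

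Two other inferences are tempting. One is that a miss on this row would block the next trial: section 2.1 is conditional on feasibility in general, there is no row-level go/no-go rule, and the analysis is descriptive. The other is that non-wear alone would pass the row: the 73-74% needs both zeros in the percentile and worn-day scoring, and falls short over 10 weeks. Under that rule, about 75% over 10 weeks takes some 30% untracked days, which would itself miss the tracking benchmark.

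**Conclusion.** The point holds as one of interpretation and specification. The row carries information about follow-through, but neither a pass nor a miss at 75% shows by itself whether the step goal is feasible. With full wear, none of the no-change scenarios examined comes near 75%, and a large steady rise moves the score by only about 6 points. The exact rates depend on assumed step levels, day-to-day variation and percentile formula; the conclusion does not change across the ranges shown. The top-up example in step 4 depends on its response model, so its direction matters more than its size.

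The missing untracked-day rule is a separate gap and stands even if 75% is accepted as an ambitious target: at 25% untracked it moves the no-change score across about 35 points at the easier level (39% to 74%) and 24 at the harder (29% to 53%).

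Severity is minor to moderate: the row is not exploratory, but it is one of several and no single row is decisive.

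**What to change.** Leave the step-goal rule and the 75% figure as they are. In 3.6.2 and 3.9:

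- State the percentile formula and whether untracked days entered the delivered goals. When computing the reference below, leave untracked days out of the percentile unless the delivered goals did otherwise.
- State the attainment denominator, and show both worn-day and all-day results.
- Report step attainment separately by level, with week 1 apart from weeks 2-10, beside that level's no-change rate under the actual rule.
- Compute the no-change rate from each participant's within-week or detrended day-to-day variation. Shuffling all 70 days mixes any trend into the reference: in a check with 16 participants per level, a rise of 500 steps/day each week stood only 3 to 6 points above a shuffled reference, against chance variation of up to about 3.3 points either way.
- Beside it, report change in mean daily steps and the percentage of days meeting the fixed week-1 goal. Read the latter within level, since the harder week-1 goal is 1,500 steps higher.
- Say that the 75% for weeks 2-10 is interpreted together with these figures, and that the raw easier-harder gap is not a feasibility difference.

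**Cost.** A note on one row and a few sentences, using step data already collected. The downsides are slightly more reporting, a less simple benchmark row, and a reference rate that rests on stated assumptions. Under section 3.7.4 the change needs IRB approval and a registry update.

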3.6 Outcomes

3.6.1 Overview of Measures

The primary outcomes of this pilot study relate to the feasibility and acceptability of the various goals and their intensity levels. We will compare these outcomes to our a priori benchmarks listed in the **Table** below. Additional exploratory outcomes are also included in this table, and marked with an asterisk. The planned primary outcome for the subsequent fully-powered optimization trial is weight change. We will collect data on weight change in our pilot study. Based on prior research of digital weight loss interventions, we have set benchmarks for the 3% and 5% thresholds, which have been associated with improved cardiometabolic health. We will measure body weight using smart scales (Fitbit Aria Air) that automatically transmit data to the research team. The smart scales will be mailed to participants. Participants will be provided with best practices prior to each weight assessment: calibrate upon arrival; weigh in the AM without clothing, before eating/drinking, and after voiding. We will also administer behavior change measures that will be used in the subsequent optimization trial. In particular, dietary recalls will be measured using the Automated 24-Hour (ASA-24) Dietary Assessment Tool and physical activity will be measured using the GLTEQ self-report measure as well as objectively via the Fitbit Inspire 3 activity tracker to evaluate step count. We will also assess perceived ease of the goals.

